# 9.4 Renal safety monitoring

Every renal laboratory trigger or renal event must be followed up by the investigator or designated personnel at the trial site. Recommended follow-up assessments are listed in Appendix 2.

All follow-up information, and the procedures performed must be recorded as appropriate in the CRF. Refer to the Site Operations Manual for additional details.

# 9.5 Reporting of study treatment errors including misuse/abuse

Medication errors are unintentional errors in the prescribing, dispensing, administration or monitoring of a medicine while under the control of a healthcare professional, patient/subject or consumer (EMA definition).

Misuse refers to situations where the medicinal product is intentionally and inappropriately used not in accordance with the protocol.

Abuse corresponds to the persistent or sporadic, intentional excessive use of a medicinal product, which is accompanied by harmful physical or psychological effects.

All study treatment errors and uses outside of what is foreseen in the protocol will be collected in the dose administration record (DAR) CRF. Study treatment errors are only to be reported to Chief Medical Office and Patient Safety (CMO& PS) department if the treatment error is associated with an SAE.

All instances of misuse or abuse must be documented in the adverse event (AE) CRF irrespective of the misuse/abuse being associated with an AE/SAE. In addition, all instances of misuse or abuse must be reported to Novartis Chief Medical Office and Patient Safety (CMO& PS). As such, instances of misuse or abuse are also to be reported using the SAE form/CRF. Table 9-1 summarizes the reporting requirements.

Treatment error type	Document in Dose Administration (DAR) CRF	Document in AE CRF	Complete SAE form/CRF
Unintentional study treatment error	Yes	Only if associated with an AE	Only if associated with an SAE
Misuse/Abuse	Yes	Yes	Yes, even if not associated with a SAE

 Table 9-1
 Guidance for capturing study treatment errors

For more information on AE and SAE definition and reporting requirements, please see Section 9.1 and Section 9.2, respectively.

### 9.6 **Pregnancy reporting**

Reproductive toxicity and teratogenicity data are not available for the investigational drug at this time, therefore no guidelines on therapeutic recommendations in case of pregnancy are available. This study enrolls women on highly effective birth control and who are considered not to be of childbearing potential, thus pregnancy is not an expected outcome for any female study participant. However, in the case that a pregnancy in a female study participant should occur, please follow the below reporting guidelines.

To ensure subject safety, each pregnancy occurring after signing the informed consent must be **reported to Novartis within 24 hours** of learning of its occurrence. The pregnancy should be followed up to determine outcome, including spontaneous or voluntary termination, details of the birth, and the presence or absence of any birth defects, congenital abnormalities, or maternal and/or newborn complications.

Pregnancy must be recorded on the Pharmacovigilance Pregnancy Form and reported by the investigator to the local Novartis Chief Medical Office and Patient Safety (CMO&PS) Department. Pregnancy follow-up should be recorded on the same form and should include an assessment of the possible relationship to the study treatment.

Any SAE experienced during the pregnancy and unrelated to the pregnancy must be reported on an SAE form.

The study drug must be discontinued though the subject may stay in the study, if she wishes to do so. All assessments that are considered as a risk during pregnancy must not be performed. The subject may continue all other protocol assessments.

# 9.7 **Prospective suicidality assessment**

Not applicable.

# 9.8 Early phase safety monitoring

The investigator will monitor adverse events in an ongoing manner and inform the Sponsor of any clinically relevant observations. Any required safety reviews will be made jointly between medically qualified personnel representing the sponsor and investigator. Such evaluations may occur verbally, but the outcome and key discussion points will be summarized in writing (email) and made available to both sponsor and all investigator(s). Criteria pertaining to stopping the study/treatment or adapting the study design are presented above.

When two or more clinical site(s) are participating in the clinical study, the sponsor will advise the investigator(s) at all sites in writing (email) and by telephone, if possible, of any new clinically relevant safety information reported from another site during the conduct of the study in a timely manner.

# **10** Data review and database management

# 10.1 Site monitoring

Before study initiation, at a site initiation visit or at an Investigator's Meeting, a Novartis representative will review the protocol and data capture requirements (i.e. eSource or eCRFs) with the investigators and their staff. During the study Novartis employs several methods of ensuring protocol and GCP compliance and the quality/integrity of the sites' data. The monitor will visit the site to check the completeness of subject records, the accuracy of data capture / data entry, the adherence to the protocol and to Good Clinical Practice, the progress of enrollment, and ensure that study drug is being stored, dispensed, and accounted for according to specifications. Key study personnel must be available to assist the monitor during these visits.

Continuous remote monitoring of each site's data may be performed by Novartis or CRO working on behalf of Novartis. Additionally, a central analytics organization may analyze data and identify risks & trends for site operational parameters, and provide reports to Novartis Clinical Teams to assist with trial oversight.

The investigator must maintain source documents for each subject in the study, consisting of case and visit notes (hospital or clinic medical records) containing demographic and medical

information, laboratory data, electrocardiograms, and the results of any other tests or assessments. All information on CRFs must be traceable to these source documents in the subject's file. The investigator must also keep the original informed consent form signed by the subject (a signed copy is given to the subject).

Confidential

The investigator must give the monitor access to all relevant source documents to confirm their consistency with the data capture and/or data entry. Novartis monitoring standards require full verification for the presence of informed consent, adherence to the inclusion/exclusion criteria, documentation of SAEs, and the recording of data that will be used for all primary and safety variables. Additional checks of the consistency of the source data with the CRFs are performed according to the study-specific monitoring plan. No information in source documents about the identity of the subjects will be disclosed.

# **10.2** Data collection

Designated investigator staff will enter the data required by the protocol into the Electronic Case Report Forms using fully validated software that conforms to 21 CFR Part 11 requirements. Designated investigator site staff will not be given access to the EDC system until they have been trained. Automatic validation programs check for data discrepancies and, by generating appropriate error messages, allow the data to be confirmed or corrected before transfer of the data to the CRO working on behalf of Novartis. The investigator must certify that the data entered into the Electronic Case Report Forms are complete and accurate. After database lock, the investigator will receive copies of the subject data for archiving at the investigational site.

All data captured for this study will have an external originating source (either written or electronic) with the CRF not being considered as source.

All data should be recorded, handled and stored in a way that allows its accurate reporting, interpretation and verification.

### **10.3** Database management and quality control

The CRO, working on behalf of Novartis will review the data entered into the CRFs by investigational staff for completeness and accuracy and instruct the site personnel to make any required corrections or additions. Queries are sent to the investigational site using an electronic data query. Designated investigator site staff is required to respond to the query and confirm or correct the data. If the electronic query system is not used, a paper Data Query Form will be faxed to the site. Site personnel will complete and sign the faxed copy and fax it back to the CRO, working on behalf of Novartis, who will make the correction to the database. The signed copy of the Data Query Form is kept at the investigator site.

Concomitant medications entered into the database will be coded using the WHO Drug Reference List, which employs the Anatomical Therapeutic Chemical classification system. Medical history/current medical conditions and adverse events will be coded using the Medical dictionary for regulatory activities (MedDRA) terminology.

Laboratory samples will be processed centrally and the results will be sent electronically to Novartis (or a designated CRO).

Novartis
Amended Protocol Version v08 (Clean)

Randomization codes and data about all study drug(s) dispensed to the subject and all dosage changes will be tracked using an Interactive Response Technology (IRT). The system will be supplied by a vendor, who will also manage the database. The database will be sent electronically to Novartis (or a designated CRO).

Confidential

Each occurrence of a code break via IRT will be reported to the clinical team and monitor. The code break functionality will remain available until study shut down or upon request of Novartis.

The occurrence of relevant protocol deviations will be determined. After these actions have been completed and the database has been declared to be complete and accurate, it will be locked and the treatment codes will be unblinded and made available for data analysis. Any changes to the database after that time can only be made after written agreement by Novartis management.

Commercially Confidential Information

# **10.4 Data Monitoring Committee**

Not required.

# **10.5** Adjudication Committee

Not required.

# 11 Data analysis

The analysis will be conducted on all subject data at the time the trial ends. Any data analysis carried out independently by the investigator should be submitted to Novartis before publication or presentation.

### 11.1 Analysis sets

For all analysis sets, subjects will be analyzed according to the study treatment(s) received.

The safety analysis set will include all subjects who received any study drug.

The PK analysis set will include all subjects with at least one available valid (i.e. not flagged for exclusion) PK concentration measurement, who received any study drug and with no protocol deviations with relevant impact on PK data.

The PD analysis set will include all subjects with available PD data and no protocol deviations with relevant impact on PD data. Data collected after a change of the background therapy not

Novartis	Confidential	Page 82
Amended Protocol Version v08 (Clean)		Protocol No. CCMK389X2201

based on the CSE algorithm (see Section 3.1) will be excluded from the analysis set if assessed as having a potentially relevant impact on PD.

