### Sponsor staff or delegate

The following unblinded sponsor roles are required for this study:

Unblinded clinical staff managing drug re-supply to site

Unblinded sample analyst(s) (PK, CCI )

Commercially Confidential Information

The sample analysts will receive a copy of the randomization schedule (via request to the Randomization Office), to facilitate analysis of the samples. The sample analysts will provide the sample data to the study team under blinded conditions unless otherwise allowed.

The study statistician will be able to access the randomization list for interim analyses and is allowed to share unblinded information with the rest of the clinical trial team (CTT) as appropriate for internal decision purposes, as outlined in Table 6-2. For example, unblinded summaries and unblinded individual data can be shared with the team for interim analyses.

Study programmers and other personnel involved in study data analysis CCI are allowed to access treatment assignment information for the purpose of conducting interim analyses.

The CTT is allowed to share unblinded results with other sponsor staff (e.g. decision boards) as required for internal decision making on the study or the project at the time of interim analyses while the study is ongoing.

All unblinded personnel will otherwise keep randomization lists and data or information that could unblind other study team members confidential and secure except as described above.

Following final database lock all roles may be considered unblinded.

Role		Time or E	vent	
	Randomization list generated	Treatment allocation & dosing	Safety event (single subject unblinded)	
Subjects/Patients	В	В	UI	
Site staff	В	В	UI	
Unblinded site staff (see text for details)	В	UI	UI	
Drug Supply and Randomization Office	UI	UI	UI	CCI
Unblinded sponsor staff (see text for details)	В	UI	UI	
Statistician/statistical programmer/data analysts	В	В	UI	
All other sponsor staff not identified above	В	В	UI	

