### 11.4 Analysis of the primary variable(s)

The primary aim of the study is to compare the effect of CMK389 versus placebo on the clinical disease activity of sarcoidosis patients as measured by the change from baseline in the percent predicted FVC at week 16 in the PD population. This will be assessed regardless by the background steroid dose and assuming all patients remained on their treatment throughout the study.

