#### 11.4.2 Statistical model, hypothesis, and method of analysis

The change from baseline in percent predicted FVC will be analyzed using a Bayesian model for repeated measurements. The model will investigate effects for treatment by time (included as a class variable) interaction, baseline FVC by time interaction, prior sarcoidosis immunosuppressant therapy (stratification factor) and baseline prednisone dose. The correlation among the repeated measures collected on the same subject will be assessed via an unstructured covariance matrix. The stratification factor may be removed in case of strata with low sample sizes impacting on the convergence of the model.

Uninformative priors will be utilized to obtain the posterior estimates. Baseline is defined as Day 1.

The posterior probability that CMK389 is better than placebo in terms of change from baseline in percent predicted FVC at 16 weeks will be calculated. If it is at least 90%, it will be considered a sign of efficacy of CMK389 in this patient population.

The primary analysis will include all available data from patients in the PD analysis set with baseline and at least one post baseline assessment.

A supplementary analysis may be conducted including also FVC values collected after a change of the background therapy not based on the CSD algorithm.

Novartis	Confidential	Page 83
Amended Protocol Version v08 (Clean)		Protocol No. CCMK389X2201

If data permits, additional subgroup analysis of the primary endpoint will be conducted for the following three subgroups: increased, no change and decreased prednisone dose at week 16 compared to baseline.

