INCL01	Deviation from inclusion criteria: Written informed consent was not obtained before any study assessment was performed	Yes
TRT01	Treatment deviation with impact on PD data	Yes
TRT02	Treatment deviation with impact on PD data from a timepoint onwards	Yes from a timepoint onwards
OTH01	Other deviation with impact on PD data	Yes
OTH02	Other deviation with impact on PD data from a timepoint onwards	Yes, from a timepoint onwards

Category Deviation code	Text description of deviation	Data exclusion
OTH04	Impact on spirometry and DLCO at a specific time point	Yes, at a specific timepoint only.
OTH12	Impact on spirometry at a specific time point	Yes, at a specific timepoint only.
OTH13	Impact on DLCO at a specific time point	Yes, at a specific timepoint only.
CMD02	Prohibited concomitant medication used with a relevant impact on efficacy endpoint	Yes, from a timepoint onwards
INCL04	Deviation from inclusion criteria: No biopsy proven pulmonary sarcoidosis diagnosed > 1 year prior to screening	Yes
INCL06	Deviation from inclusion criteria: HRCT <= 15% reticular volume at screening	Yes
EXCL05	Deviation from exclusion criteria: FVC < 50% at screening	Yes
EXCL06	Deviation from exclusion criteria: mMRC dyspnea scale >= 3 at screening	Yes
EXCL27	Deviation from exclusion criteria: deteriorated during Run-in	Yes

If updates to this table are needed, an amendment to the SAP needs to be implemented prior to DBL.

All DLCO related parameters will be excluded at specific visit only if the condition below is encountered: DLCO % change (absolute value) vs previous assessment > 35% or % change in alveolar volume vs previous assessment > 20%.

DLCO related parameters are: DLCO (absolute value and % predicted), ALVVOL (alveolar volume), DLCOHCCP (corrected by Hg), DLCOVA (/ volume), CPID (CPI = it includes DLCO).

5 Statistical methods for Pharmacokinetic (PK) parameters

All subjects within the PK analysis set will be included in the PK data analysis.

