6.1.1 Variables

The primary variable will be the change from baseline in percent predicted FVC at Week 16. The FVC is measured at screening, day 1, week 4, week 8, week 12, and week 16. Baseline is defined as day 1.

For the primary analysis, the only data quality condition affecting data inclusion to the analysis will be that the number of accepted tests is greater than zero. No other flags related to quality

will lead to an exclusion of records Also, the main efficacy analysis will exclude all the data collected after a steroid dose increase NOT driven by the algorithm.

These cases will be detected programmatically and will be reconciled by manual checks. Should it become not feasible to detect all cases programmatically, then the team will release an excel file with the list of events and dates. According to each case, efficacy data will be excluded at a specific visit, or will be excluded from a timepoint onwards.

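### The primary FVC analysis groups patients by treatment received and drops whole patients under two undefined deviation codes, with no as-randomised analysis planned to check the result

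*Protocol*

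**What the plan says.** **Grouping.** Protocol 11.1 opens with "For all analysis sets, subjects will be analyzed according to the study treatment(s) received", and SAP section 4 repeats it. Neither makes an exception for efficacy.

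**Population for the primary analysis.** Protocol 11.4 defines the primary comparison "as measured by the change from baseline in the percent predicted FVC at week 16 in the PD population", and SAP 6.1 agrees. Protocol 11.4.2 adds a data condition: "The primary analysis will include all available data from patients in the PD analysis set with baseline and at least one post baseline assessment".

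**Who is left out.** Protocol 11.1: "The PD analysis set will include all subjects with available PD data and no protocol deviations with relevant impact on PD data". SAP Table 4-1 puts this into codes of three kinds:

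- TRT01 ("Treatment deviation with impact on PD data") and OTH01 ("Other deviation with impact on PD data") remove the whole patient.
- INCL01, INCL04, INCL06, EXCL05, EXCL06 and EXCL27 also remove the whole patient, but concern consent or status before randomisation.
- TRT02, OTH02 and CMD02 keep the patient and drop data from a timepoint onwards. OTH04, OTH12 and OTH13 drop single visits.

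**Other analyses.** The supplementary analyses in Protocol 11.4.2 and SAP 6.1.5 are optional. They bring back FVC values recorded after background-therapy changes, or drop records with quality flags. None restores an excluded patient or the randomised grouping.

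**Safeguards.** Protocol 10.3 has relevant deviations determined before the database is locked and the codes are unblinded. A change to Table 4-1 needs a SAP amendment before lock.

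**The concern.** Treatment received is the usual grouping for safety and PK. For efficacy, Protocol 3.2 itself says that randomisation underlies the assumptions of the statistical tests. That support weakens when patients can be regrouped, or removed for events that follow randomisation.

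Of the two, removal matters more. A deviation can be a consequence of treatment. Protocol 6.6 does not permit missed doses, and Protocol 7.2 makes a missed dose or a severe infection a reason to stop study treatment. A missed dose could reasonably be coded as a treatment deviation, and the reason behind it may differ by arm. Blinded coding does not cure this: the coder can be unaware of the arm while the event still depends on it.

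The codes also leave room for judgement. Table 4-1 gives no criterion for TRT01 or OTH01 beyond an impact on PD data, and does not say when a deviation takes the whole patient (TRT01, OTH01) rather than later data only (TRT02, OTH02). The amendment rule fixes the list of codes, not which patients receive them.

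At stake is a go/no-go criterion, a posterior probability of at least 90%, applied to about 56 patients. Two or three exclusions can matter at that size.

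**Working it through.** **Inputs (Protocol 11.7).** 66 randomised 1:1; about 15% dropout; 28 per arm with week-16 data; SD 9 points; true difference 5 points; success if the posterior probability is at least 90%; stated power about 80%; stated false-positive rate 10%.

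**Reproducing the plan's figures.** With uninformative priors, a 90% posterior probability behaves like a one-sided 10% test, with critical value 1.2816.

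- Evaluable patients: 66 × 0.85 = 56.1, or 28 per arm.
- SE = 9 × √(2/28) = 2.405.
- Power = Φ(5/2.405 − 1.2816) = Φ(0.797) = 78.7%, which fits the stated 80% or so.
- False-positive rate with no bias = Φ(−1.2816) = 10%.

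**Effect of selective exclusion when the drug does nothing.** The documents give no number, direction or selectivity of exclusions, so these are assumptions: three patients are excluded in total, and those excluded average 1 SD (9 points) below their own arm. With a excluded from active and p from placebo:

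- shift = 9a/(28 − a) − 9p/(28 − p)
- SE = 9 × √(1/(28 − a) + 1/(28 − p))
- chance of meeting the criterion = Φ(shift/SE − 1.2816)

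| Excluded, active / placebo | Shift (points) | SE | Chance of meeting the criterion |
|---|---|---|---|
| 3 / 0 | 27/25 = +1.08 | 2.476 | Φ(−0.845) = 19.9% |
| 2 / 1 | 18/26 − 9/27 = +0.36 | 2.473 | Φ(−1.136) = 12.8% |
| 1 / 2 | −0.36 | 2.473 | Φ(−1.427) = 7.7% |
| 0 / 3 | −1.08 | 2.476 | Φ(−1.718) = 4.3% |

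With all exclusions in the active arm, two patients give 15.9% and four give 24.7%.

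**Balanced, non-selective exclusion.** With three fewer per arm, SE = 9 × √(2/25) = 2.546 and power = Φ(5/2.546 − 1.2816) = Φ(0.683) = 75.3%. The cost is 78.7 − 75.3 = 3.4 points of power, and the false-positive rate stays at 10%.

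**The case against.** The case for leaving the plan alone is substantial.

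- **Grouping by treatment received will rarely matter.** It changes the result only if a patient gets the wrong arm. Allocation reaches an unblinded pharmacist through the NIRT system (Protocol 6.4), and site staff give and record every dose (Protocol 6.8). This stands; exclusions are the main issue.
- **Most whole-patient codes are not post-randomisation, and dated deviations have their own codes.** This also stands. It narrows the point to TRT01 and OTH01, which can arise after randomisation but need not.
- **Deviations are settled before lock and unblinding.** True, and a real protection against choosing exclusions by result. It does not protect against deviations that treatment itself brings about.
- **The study is a non-confirmatory proof of concept, and its primary question is framed as if all patients had stayed on treatment.** This bears on how serious the point is. It does not explain why no analysis with the excluded patients is planned.

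A reader might infer three stronger things that the documents do not support.

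- *That exclusions will be chosen by people who have seen unblinded data.* Protocol 6.4 says that the study statistician "is allowed to share unblinded information with the rest of the clinical trial team (CTT) as appropriate", and its example covers individual data at interim analyses. But whether and when an interim takes place, and any separation of roles, is redacted. Access is permitted; nothing shows that it occurs or that it reaches whoever assigns the codes.
- *That SAP 6.1.1 lets the team list patients to drop.* The words "then the team will release an excel file with the list of events and dates" describe a fallback for finding steroid increases outside the algorithm when programming cannot. They do not concern TRT01 or OTH01.
- *That the 10% rate is lost, or becomes 20%.* The 20% needs all three exclusions in the active arm and all well below its mean. Other splits of the same three patients give 13%, 8% or 4%.

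**Conclusion.** The concern holds in limited form. The primary comparison rests on a set grouped by treatment received, from which whole patients can be removed under two codes without objective criteria, and no as-randomised efficacy analysis that includes them appears in the available text. The 10% false-positive rate is conditional on exclusions being unrelated to arm and outcome.

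The size cannot be known from the documents. Under the assumptions above, three selective exclusions move the rate anywhere from about 4% to about 20%, and balanced non-selective ones cost 3.4 points of power. The bias could run against the drug as easily as for it. For a non-confirmatory study with deviations settled before unblinding, this is an improvement that should be made, not a flaw that invalidates the design.

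**What to change.** 1. In Protocol 11.1 and SAP section 4, group patients as randomised for efficacy. Keep treatment received for the safety and PK sets.
2. Add one mandatory sensitivity run of the SAP 6.1.3 model on all randomised and dosed patients with a baseline and at least one post-baseline FVC. Of the whole-patient exclusions, keep only INCL01, because consent was not obtained before assessments; lift TRT01, OTH01 and the other entry-deviation codes. Report it beside the PD-set result. The timepoint and single-visit data rules can stay as they are, so that the two runs differ only in who is included and how they are grouped.
3. State in the SAP that TRT01 and OTH01 are assigned before database lock by staff with no access to allocation or unblinded interim data. They cannot all be assigned before an interim look, since later deviations will not yet have happened.

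The cost is one extra model run, SAP text, and a wording change in Protocol 11.1 that can wait for the next amendment, because Protocol 13.1 requires formal approval. The statistical downside is slight dilution of the estimated effect if a patient is mis-dosed. If the two results agree, the proof-of-concept decision is stronger; if they differ, those deciding need to know.
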